1.0 Background /Introduction

Canadian military and veteran populations experience elevated rates of the risk factors associated with committing or being the victim of intimate partner violence (IPV). Relative to the general population, Canadian military and veteran populations are more likely to report a history of child maltreatment exposure (1), as well as substance and mental health-related challenges related to deployment, re-deployment, and combat exposure (2); each of these experiences has been found to be associated with the likelihood of IPV perpetration or victimization (3-7). Population-level estimates of IPV prevalence among Canadian veterans—which include retired/discharged members of the Canadian Armed Forces (CAF; Royal Canadian Navy, Canadian Army, and Royal Canadian Air Force) and retired members of Royal Canadian Mounted Police—are not available. However, a recent systematic review and meta-analysis of predominately American studies showed that one in eight active duty personnel and veterans self-report perpetrating IPV in their intimate relationship and one in five report recent IPV victimization (8). Similarly, approximately 30% of individuals who are members of the CAF or whose partner is a member of the CAF self-report IPV victimization (9, 10). By extension, this indicates that at the population level, close to one-third of CAF veterans or their partners, will experience some form of IPV victimization in their lifetime and this proportion is likely an underestimate.

Healthcare and social service providers (HSSP) who work with veteran populations have an important role in the prevention of IPV recurrence and associated impairment (11, 12). However, increasing evidence (13-24) indicates that generally, HSSPs receive insufficient training related to recognizing and responding to IPV in their clinical encounters; providers report discomfort initiating conversations about IPV, a lack of time to adequately recognize and respond to disclosures, and challenges with determining appropriate referrals and reporting requirements. These challenges can be exacerbated in the context of veteran populations given unique healthcare and social service structures and stigma related to disclosing IPV. It is also important to note that the optimal approach for preparing HSSPs with the knowledge and skills to effectively recognize and respond to IPV, remains unclear. Educational interventions that have been evaluated vary in their instructional approaches and fail to consider active controls (i.e., comparator programs that also focus on IPV, but use different instructional methods). They also tend to focus on physical and sexual IPV, as well as screening; this is despite evidence and statements from the World Health Organization, the National Institute of Health and Care Excellence and the Canadian Task Force on Preventive Health Care that indicate there is no evidence that universal screening for IPV reduces IPV recurrence or improves the health outcomes of individuals exposed to IPV. Finally, few educational interventions acknowledge the complex overlap between IPV, children's exposure to IPV, and other forms of family violence, including child physical, sexual, and emotional abuse and neglect (25). Collectively, this information indicates an urgent need for educational interventions and associated evaluations that address all forms of IPV and related forms of family violence, across healthcare and social service disciplines working with veteran members, and which provide evidence for the optimal educational approach for improving provider knowledge and skills to effectively recognize and respond to IPV.

1.1 Overview and Rationale for Selection of Violence, Evidence, Guidance, Action Project (VEGA) Education Intervention

The Violence, Evidence, Guidance, Action (VEGA) Education Resources¹ are a novel education intervention that has the potential to improve the preparation of healthcare and social service providers (HHSPs) to be able to effectively recognize and respond to IPV and related forms of family violence, including child maltreatment (CM), in their clinical encounters. VEGA resources were developed based on systematic reviews and consultation with individuals belonging to 22 national healthcare and social service organizations, including the Royal College of Physicians and Surgeons of Canada (see www.vegaproject.mcmaster.ca). VEGA resources follow a competency-based framework and a participatory, encounter-based curriculum that includes four learning modules: (a) the epidemiology of IPV and CM; (b) strategies for safely recognizing and responding to (i) IPV and (ii) CM; and (c) principles for ensuring safe clinical encounters for IPV and CM discussions. VEGA can be completed as a self-directed learning opportunity or in a workshop that is led by two trained facilitators; both approaches take approximately 3.5 hours to complete. *Importantly, neither of the VEGA educational approaches have been evaluated as an adjunct to standard HSSP education for improving HSSP knowledge and skills related to IPV.*

¹Used with permission from the VEGA Project.

2.0 Study Design

2.1 Study objectives

The overall goal of this study is to determine the acceptability and feasibility of administering the VEGA intervention to Canadian veteran service providers, adjunct to standard HHSP education. We also aim to generate initial estimates of the effectiveness of the VEGA resources for improving knowledge and skills for recognizing and responding to IPV and CM in this population. Our initial secondary objective was to contribute to the knowledge base regarding the optimal educational approach for education in IPV and CM among veteran-serving HSSPs. These objectives were to be achieved by conducting a two-arm pilot randomized controlled trial of 80 veteran-serving HHSPs that compares the two educational approaches: self-directed VEGA (experimental arm) and facilitator-led VEGA (active control arm).

As of March 2023, after consulting with our collaborators at the Atlas Institute, we are moving to a one-arm pilot trial of the self-directed VEGA resources. Due to low enrollment, we want to focus on our primary aim which is to deliver the VEGA resources to this population of HHSPs. Facilitator-led VEGA requires a minimum number of participants in order to move forward with a single workshop which is proving harder to achieve given the longstanding infrastructure challenges related to the COVID-19 pandemic for front-line service providers and their schedules. With support from our collaborators at Atlas, we are now restricting our intervention delivery to the self-directed VEGA resources given the freedom with which participants can complete the intervention independently with varying schedules.

We are now focusing on achieving sample size aims for one of the two arms of the study and no longer going to evaluate the facilitator-led VEGA. Our primary aim will be achieved by

conducting a one-arm pilot trial of 40 veteran-serving HHSPs where participants will complete self-directed VEGA.

2.1.1 Two arm pilot randomized controlled trial (February 2022 to May 2023).

Primary outcomes of feasibility will be obtained by the RC tracking the recruitment and administration of the VEGA resources. The perceived acceptability and impact of the approaches will be determined by qualitative interviews conducted in a sub-sample of participants. The evaluation of secondary outcomes will be powered to detect moderate self-reported improvements in IPV and CM knowledge and skills, as well as preparedness and self-efficacy related to recognizing and responding to IPV and CM. These secondary outcomes will be obtained via self-report surveys administered at baseline (Time 1), post-education (Time 2), and at 3-month follow-up time points (Time 3).

2.1.2 Mixed Method Research Design.

We will use the embedded-experiment (QUAN(qual)) mixed method research design (26, 27). A strand of quantitative data collection will provide important acceptability and feasibility metrics related to enrollment, retention, attrition, data completeness, as well as exploratory estimates of education effect for the VEGA resources. The qualitative strand of data collection will generate important contextual information regarding the tenability of an RCT, the perceived value and impact of the VEGA resources and examine the *why* of acceptability and feasibility, as well as educational impact (or not) from the perspective of veteran-service providers.

2.1.3 Primary and Secondary Aims

Primary Aims: To determine the feasibility and acceptability of an RCT comparing two VEGA educational approaches, the self-directed vs facilitator-led VEGA, in HHSPs who serve veterans and their families. To determine the feasibility of the RCT we will use four outcomes: (i) the number of HHSPs who meet eligibility criteria and (ii) who agree to be randomized to either self-directed or facilitator-led VEGA education approaches, both overall and per week of recruitment, (iii) the proportion of HHSPs who complete each arm, with completion consisting of the review of all module content and the animated simulations in the case of self-directed VEGA and full attendance of the virtual workshop in the case of facilitator-led VEGA and (iv) the feasibility of collecting trial outcome data at Time 1, Time 2, and Time 3. The acceptability of the facilitator-led and self-directed educational approaches as well as their value and impact will be determined via the coding of qualitative interview data from a sub-sample of participants.

Our aims are that (i) we will recruit, on average, 5 providers per week and achieve our sample aims of 80 participants within 16 weeks, (ii) the proportion of providers who contact the research team about participation and who consent to randomization will be 70% or greater, (iii) the proportion of providers who are randomized and complete their assigned intervention will be 70% or greater for each arm and (iv) the proportion of missing data for each time-point will be less than 20%.

Centre of Excellence VEGA Training and Research Project

As of March 2023, we will revise primary outcomes (ii) and (iii) to (ii) the number of HHSPs who consent to participate in the study and complete self-directed VEGA, both overall and per week of recruitment, (iii) the proportion of HHSPs who complete self-directed VEGA, with completion consisting of the review of all module content and the animated simulations in the case of self-directed VEGA. Our aims are (ii) the proportion of providers who contact the research team about participation and who consent to participate will be 70% or greater and (iii) the proportion of providers who complete self-directed VEGA will be 70% or greater.

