2.2.3 Randomization

Centre of Excellence VEGA Training and Research Project

Randomization will occur after consent has been obtained and the web-based baseline (Time 1) survey is complete. As indicated in the previous section, randomization will occur five business days before the facilitator-led VEGA session the participant is available to attend is scheduled. Participants will be randomly assigned to one of the two conditions using stratified block randomization, with a block size of 4 (blocking factor of 2), using an internet-based randomization service; <https://www.randomize.net/>. Randomization will be stratified based on sex at birth with two levels to this variable: female and male.

Participants will be informed of their treatment arm status by the RC. The RC will not reveal participant allocations to the RA who will be directly involved in the quantitative data collection. Participants will also be encouraged not to inform the RA of their allocation.

As of March 2023, participants will not be randomized to complete either facilitator-led or self-directed VEGA, all participants will be asked to complete self-directed VEGA.

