4.2 Sample Size

We will recruit a voluntary sample of 80 HHSPs that will be randomized to either the experimental or AC arm. We have selected this sample size given previous work which indicates that 40 HSSPs per arm would provide 80% power to detect a moderate (0.5 SD – to – 0.6 SD) effect size, which is indicative of a clinically significant outcome (40).

As of March 2023, we are now focusing on achieving sample size aims for one of the two arms of the study and no longer going to evaluate the facilitator-led VEGA. Our primary aim will be achieved by conducting a one-arm pilot trial of 40 veteran-serving HHSPs where participants will complete self-directed VEGA. In following this algorithm, our team will be able to consider the needed recruitment and retention rates to successfully implement a definitive education trial.

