4.4 Integration of Qualitative and Quantitative Data for Interpretation

After conducting separate quantitative and qualitative analyses, quantitative and qualitative data will be integrated for interpretation. Quantitative acceptability and feasibility metrics will be mapped to excerpts of qualitative data on perceived acceptability or educational burden via a mixed method joint display; this display will support a comprehensive interpretation of the extent to which a definitive trial examining VEGA in our sample population is tenable. A separate joint display will cross-tabulate scores on secondary outcome measures with qualitative excerpts of VEGAs perceived value and impact for improving provider knowledge and skills related to IPV and CM alongside a narrative description of findings that integrates our conceptual frameworks for continuing education among HSSPs working with or who have worked with the veteran population (41-43).

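### Section 2.1.3 still sets RCT feasibility as the primary aim, but the revised one-arm criteria say nothing about willingness to be randomised or about workshop completion

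*Combined protocol and SAP*

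**What the plan says.** **Primary aim.** Section 2.1.3 states it as "To determine the feasibility and acceptability of an RCT comparing two VEGA educational approaches" and lists four feasibility outcomes for that RCT. The March 2023 paragraph in the same section revises outcomes (ii) and (iii) only. The aim sentence and outcomes (i) and (iv) are untouched.

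**A second account of the aim.** The March 2023 text in Section 2.1 reads "Due to low enrollment, we want to focus on our primary aim which is to deliver the VEGA resources to this population of HHSPs". It adds that facilitator-led VEGA will no longer be evaluated and that the aim will be met with a one-arm trial of 40.

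**Criterion (ii) before the change:** "the proportion of providers who contact the research team about participation and who consent to randomization will be 70% or greater".

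**Criterion (ii) after the change:** "the proportion of providers who contact the research team about participation and who consent to participate will be 70% or greater".

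**Criterion (iii)** was at least 70% completion in each arm. It is now at least 70% completion of self-directed VEGA.

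**Randomisation.** Section 2.2.3 says that from March 2023 "participants will not be randomized to complete either facilitator-led or self-directed VEGA, all participants will be asked to complete self-directed VEGA". Section 2.2.4 removes the facilitator-led arm.

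**Conclusions to be drawn.** Section 2.1.2 has the interviews inform whether an RCT is tenable, and Section 2.1.3 expects them to reveal no fatal flaw in running one. Section 4.2 says that "our team will be able to consider the needed recruitment and retention rates to successfully implement a definitive education trial". Section 4.4 aims at a "comprehensive interpretation of the extent to which a definitive trial examining VEGA in our sample population is tenable". None of these is limited to the one-arm design.

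**The concern.** The aim names a randomised comparison of two approaches, while the data collected after March 2023 come from one approach that everyone receives. The threshold is the same number before and after, but it is applied to a different request. Under the two-arm design a provider had to accept allocation by chance, including possible allocation to a scheduled workshop; Section 2.2.3 ties randomisation to a session the participant could attend. Under the one-arm design the provider agrees to a known online course, and Section 2.1 justifies the switch by the flexibility this gives.

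At stake is the reading of the primary result. If the plan is followed as written, a consent proportion of 70% or more in the one-arm phase would be set against an RCT-feasibility aim that it does not measure. Likewise, 70% completion of the online modules would stand in for a criterion that required completion in both arms. Section 4.1.2 compares the primary outcomes with their thresholds descriptively and specifies no breakdown by enrolment period, so nothing in the plan prevents that reading.

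**Working it through.** **1. What each criterion measures**

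| | Two-arm phase | From March 2023 | Bears on an RCT of the two approaches? |
|---|---|---|---|
| (ii) consent, at least 70% of providers contacting the team | to randomisation | to participate | Revised form: no information on accepting randomisation |
| (iii) completion, at least 70% | each arm | self-directed only | Revised form: self-directed arm only, nothing on the workshop |
| (i) recruitment | 5 per week, 80 in 16 weeks | not revised | Target not adapted to 40 |
| (iv) missing data under 20% per time-point | both arms | not revised | Still informative for the self-directed approach |

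The figures in (i) agree with each other: 5 × 16 = 80. The 70% is a chosen threshold with no derivation in the documents, so there is nothing to reproduce.

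**2. Size of the gap in (ii)**

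Let c be the proportion consenting to participate and r the share of those consenters who would also accept randomisation. Then consent to randomisation = c × r. The documents do not give r and the one-arm phase cannot estimate it. The formula also assumes that anyone willing to be randomised would have joined the one-arm study.

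| r (assumed) | c = 70% | c = 80% | c needed for c × r = 70% |
|---|---|---|---|
| 1.0 | 70% | 80% | 70% |
| 0.9 | 63% | 72% | 78% |
| 0.8 | 56% | 64% | 87.5% |
| 0.7 | 49% | 56% | 100% |

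At c = 80%, the two-arm criterion is met only if r ≥ 0.70 / 0.80 = 0.875. Below r = 0.7 it cannot be met at any c.

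**3. Chance of passing, at the planned size**

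Forty consenters at 70% imply about 40 / 0.70 = 57 contacts (assumed; the documents give no number of contacts). The observed proportion would be 40/57 = 70.2%, Wilson 95% interval 57% to 80%. With X binomial(57, p), P(X ≥ 40) is:

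- p = 0.80 (c = 80%, revised criterion): 0.97
- p = 0.72 (r = 0.9): 0.68
- p = 0.64 (r = 0.8): 0.20
- p = 0.56 (r = 0.7): 0.02

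A near-certain pass on the revised criterion is therefore compatible with a likely failure on the two-arm one.

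**4. Which participants belong to which phase**

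The heading of Section 2.1.1 dates the two-arm trial from February 2022 to May 2023, while the switch is dated March 2023. Sections 2.1 and 4.2 speak of reaching the sample size for one of the two arms, which leaves open whether participants already allocated to self-directed VEGA count towards the 40. The consent request that each participant answered is therefore not fixed by the plan.

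**The case against.** The protocol is layered: text for the two-arm design stands, and the March 2023 paragraphs override it. Read that way, Section 2.1 has already redefined the study. Its overall goal was always the feasibility of administering VEGA, and Sections 2.2, 2.2.3, 2.2.4 and 4.2 carry the switch through. Sections 4.2 and 4.4 speak of a definitive trial, not an RCT, and neither makes a pass on criterion (ii) decisive. The study is a minimal-risk pilot with descriptive primary analyses.

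Much of this stands. Dropping the arm was a legitimate choice, and the revised criteria are valid for self-directed delivery. But the override in Section 2.1.3 names outcomes (ii) and (iii) and leaves the aim sentence alone. Sections 2.1.2 and 2.1.3 keep explicit RCT conclusions, and Section 3.2.1 describes the future study as an RCT. The two accounts of the aim have to be reconciled.

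Three stronger readings are tempting, and the documents do not support them:

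- *The phases will be pooled, or the two-arm results concealed.* No section says so. Section 2.1 openly reports low enrolment and the difficulty of filling workshops, and Section 2.2 refers to separate flow figures. What is missing is any analysis by period.
- *Low enrolment shows that the two-arm consent criterion failed.* Criterion (ii) is conditional on providers who contact the team. Few contacts can coexist with a high consent proportion. No pre-amendment counts are given, and Section 2.1 attributes the problem to workshop minimums and schedules, not to refusal of randomisation.
- *Only the two-arm phase can inform a future trial.* One-arm data on survey completion, retention and self-directed completion remain relevant.

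**Conclusion.** The point holds as an internal contradiction with a consequence for the primary conclusion. The aim in Section 2.1.3 conflicts with that in Section 2.1, and after March 2023 the criteria measure the feasibility of recruiting to and delivering self-directed VEGA. They do not measure consent to randomisation or workshop completion.

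That conclusion rests on the text alone. The size is illustrative: c, r and the 57 contacts are assumptions. With c at 80%, consent to randomisation runs from 80% down to 56% as r falls from 1.0 to 0.7, and the two-arm criterion is met only at r of 87.5% or more. If some providers would have joined only for a chance of the workshop, the nesting assumption fails and the gap could be smaller. The one-arm phase cannot settle this either way.

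**What to change.** 1. In Section 2.1.3, restate the post-amendment primary aim as the feasibility of recruiting to and delivering self-directed VEGA and collecting its outcomes. Align the RCT wording in Section 2.1.2 and in the qualitative paragraph of Section 2.1.3.
2. Report the two-arm criteria (i) to (iv) for providers who contacted the team under the two-arm consent request, with counts and confidence intervals. The denominator for (ii) should be those who made contact: the number approached may be unknowable with flyers, social media and snowball referral. State where a criterion cannot be estimated, for example per-arm completion if few were randomised. Reconcile the March 2023 switch with the May 2023 date in the heading of Section 2.1.1.
3. Tabulate consent and completion by enrolment period, and do not pool consent proportions across the two consent requests.
4. In Sections 4.2 and 4.4, base statements on consent to randomisation and on facilitator-led feasibility on the two-arm phase only, and say that the one-arm phase does not establish them. One-arm data on survey completion, retention and self-directed completion may still be used for planning.

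The cost is some rewording and one extra tabulation, with no new data collection. The conclusion on RCT feasibility becomes narrower.

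### Primary feasibility aim (i) still asks for 80 participants in 16 weeks although the planned sample is now 40, and no replacement rate or window is given

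*Combined protocol and SAP*

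**What the plan says.** Section 2.1.3 lists four primary feasibility aims. Aim (i) is that "we will recruit, on average, 5 providers per week and achieve our sample aims of 80 participants within 16 weeks". This matches the two-arm plan in section 4.2: "We will recruit a voluntary sample of 80 HHSPs that will be randomized to either the experimental or AC arm".

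The plan then changed. Section 2.1 explains that enrolment was low and that the facilitator-led arm is dropped; the primary aim is now to be met by "conducting a one-arm pilot trial of 40 veteran-serving HHSPs where participants will complete self-directed VEGA". Section 4.2 repeats the figure of 40 and says that "we are now focusing on achieving sample size aims for one of the two arms of the study".

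The corresponding change to the primary outcomes, later in 2.1.3, opens "As of March 2023, we will revise primary outcomes (ii) and (iii". New thresholds follow for those two items only, beginning "Our aims are (ii) the proportion of providers who contact the research team about participation and who consent to participate will be 70% or greater", with a completion target of at least 70% after it. Aims (i) and (iv) are not mentioned. No other section gives a new total, weekly rate or recruitment window for aim (i).

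Section 4.1.2 says that the primary outcomes will be compared descriptively with the a priori thresholds.

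**The concern.** The revision in 2.1.3 is itemised by number. Aim (iv), missing data below 20% at each time point, is also left unmentioned and plainly still applies. Read the same way, aim (i) still applies too, including its total of 80. The plan then holds a primary threshold whose total belongs to a design that has been abandoned.

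Feasibility is the primary objective, and section 4.2 says that the pilot should inform the recruitment and retention rates needed for a definitive trial. The team therefore needs to know what recruitment result would count as meeting the aim. The redesign followed low enrolment, so any replacement target will be set with some knowledge of accrual. That is acceptable in a pilot if it is disclosed, but an unstated replacement leaves the reader unable to tell what was fixed in advance.

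**Working it through.** **Inputs**

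- Rate 5 per week, total 80, window 16 weeks: section 2.1.3, aim (i).
- Current planned sample 40: sections 2.1 and 4.2.
- Scope of the March 2023 revision, outcomes (ii) and (iii) only: section 2.1.3.

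**The plan's own figure**

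Rate × weeks = 5 × 16 = 80. Aim (i) is internally consistent and fits the two-arm design exactly.

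**Aim (i) at the current planned sample**

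- Share of the stated total: 40/80 = 50%.
- Rate kept: 40/5 = 8 weeks.
- Window kept: 40/16 = 2.5 per week, half the stated rate.

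**Does the choice matter?** Suppose that all 40 are recruited, at three illustrative speeds:

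| Weeks to reach 40 | Rate per week | Stated total of 80 | 40 at 5 per week (8 weeks) | 40 within 16 weeks |
|---|---|---|---|---|
| 8 | 40/8 = 5.0 | not met (50%) | met | met |
| 12 | 40/12 = 3.3 | not met (50%) | not met | met |
| 16 | 40/16 = 2.5 | not met (50%) | not met | met |

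The stated total fails in every row, whatever the speed. The rate component is met in the first row, so it is still informative. Any recruitment period longer than 8 and up to 16 weeks passes one carry-over and fails the other.

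**Timing**

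The heading of section 2.1.1 reads "Two arm pilot randomized controlled trial (February 2022 to May 2023". Depending on the days assumed, that span is 61 weeks (28 February 2022 to 1 May 2023) to 69 weeks (1 February 2022 to 31 May 2023), well beyond 16. But it labels a study phase, not a recruitment period. The documents give no recruitment start date and no accrual count, so it cannot be said how much of the 16 weeks had been used, or whether the aim had already been missed. The label also runs to May 2023 while the redesign takes effect in March 2023, so the boundary between the phases is unclear. No text says whether people enrolled before the change count toward the 40.

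**The case against.** The strongest defence is that the document keeps its two-arm text and overrides it with paragraphs dated March 2023. Read as a whole, 80 is the superseded total: aim (i) speaks of the sample aims, and sections 2.1 and 4.2 openly change those to one arm of 40. On that reading the fault is an incomplete carry-over. This has force for the total. It does not supply a rate or a window, and the wording in 2.1.3 confines the revision to (ii) and (iii).

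Several stronger conclusions are tempting, and the documents do not support them:

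- **Enrolment is capped at 40.** It is a planned sample. No rule stops enrolment there.
- **Aim (i) as a whole cannot be met or assessed.** Only the total is out of reach at n = 40. The rate of 5 per week does not depend on the sample size.
- **Recruitment cannot be interpreted.** Revised outcome (ii) still counts those who consent and complete, overall and per week of recruitment, and section 3.1.1 tracks those screened, eligible and enrolled.
- **A go/no-go decision is compromised.** No progression rule is tied to aim (i). It is one of four aims compared descriptively.
- **The team must report a failure built into the design or swap the target quietly.** The reduction to 40 and its reason are disclosed. Reporting 80 in 16 weeks as not met, if so, would be a useful finding about the two-arm trial for which it was set.
- **The replacement must be 40 in 8 weeks.** That assumes that the rate is kept and the window shortened, which the documents do not settle.

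**Conclusion.** Aim (i) is wrong as written: a primary threshold is inconsistent with the current design. It is not an arithmetic error, since 5 × 16 = 80 is correct. At the planned n = 40 the stated total can be reached only to 50%, while the rate component remains attainable. The practical gap is the missing replacement, where the two natural carry-overs differ by a factor of two (5 against 2.5 per week, or 8 against 16 weeks).

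This rests on two readings: that 40 is what the study will enrol, and that the itemised revision in 2.1.3 leaves aim (i) standing. If the total is taken as implicitly lowered to 40, the contradiction over 80 goes but the unstated rate and window remain. The point should be fixed. It does not threaten the study, because the comparison is descriptive, recruitment counts are collected anyway, and no stated decision depends on it.

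**What to change.** In section 2.1.3, add aim (i) to the March 2023 revision. For the one-arm phase, state:

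- a total of 40;
- an explicit weekly rate and window that agree with each other (keeping the stated 5 per week implies 8 weeks; another choice is open with a reason);
- the date on which the recruitment clock starts;
- whether participants enrolled before the change count toward the 40;
- when the revised target was set and what accrual had been seen by then. Section 2.2.1 cites study materials dated 12 May 2023, after the redesign, so it may no longer be possible to fix the target before any one-arm data are seen. Disclosure serves in that case.

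Report two-arm recruitment separately against 80 in 16 weeks, as met or not met, with the date that divides the phases. In section 4.1.2, correct the cross-reference as well: it points to 2.1.2 for the primary aims, which stand in 2.1.3.

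The cost is a few sentences in 2.1.3 and one extra row in the feasibility table. No new data collection is needed beyond the dates of contact and enrolment.
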